8.5.3 Primary Efficacy Variable(s)

8.5.3.1 Outcome Measures

For the primary outcome a composite outcome of all cause-death or need of invasive mechanical ventilation up to 28 days is used. For the secondary outcome (powered secondary endpoint) log transformed levels of Lactate dehydrogenase (LDH) as a surrogate marker for organ damage are used.

8.5.3.2 Safety Variables

Assessment of safety is performed for the safety set. Safety data include:

- AEs (including changes from baseline in physical examination findings)
- Clinical laboratory results
- Vital signs
- 12-lead ECGs

The safety evaluation will be based upon the review of the individual values (potentially clinically important abnormalities) and descriptive statistics (summary tables, graphics).

8.5.3.2.1 Adverse Events

The AEs will be listed per patient using MedDRA terminology (lower level term, preferred term and system organ class) and will be reported in tables summarizing the frequency of patients with AEs and AEs by treatment and body system, the number of AEs and patients with AEs by treatments and the characteristics of AEs.

For the hematology, clinical laboratory and the urine analysis deviations from the reference ranges will be summarized in frequency tables.

8.5.3.2.2 Clinical Laboratory

All relevant clinical variables obtained during screening, final examination or the clinical trial periods will be reported in appropriate tables together with descriptive statistics. Clinical laboratory findings outside of the reference range will be flagged.

8.5.3.2.3 Vital Signs

For blood pressure and pulse rate descriptive statistics will be listed by sampling times (screening and follow-up) according to the data reported in the source documents.

8.5.3.2.4 ECG

The results of the 12-lead ECG will be listed by sampling times (screening and follow-up) according to the data reported in the source documents.

8.6 Data Quality Assurance

8.6.1 Quality Assurance System

Clinical trial management activities including medical writing, regulatory submission and communication, monitoring, data management and eCRF development and safety management will follow the Standard Operating Procedures (SOP) of the CTC North or CTC North subcontractors. Statistical analysis and clinical study report writing will follow the SOPs of FGK.

The quality management system of the CTC North and FGK has been repeatedly audited by sponsors as well as by local authorities.

Standard phases of the study may be subject to audits by the quality assurance unit (QAU) of the Sponsor or CTC North.

8.6.2 Monitoring

CTC North is responsible for the overall monitoring of the clinical trial. Local partners will be subcontracted to ensure source data verification in local languages (Denmark and UK). Local CROs will be responsible for the monitoring in the US and Russia. Site qualification and site initiation visits will be performed as phone visits. A combination of remote monitoring and regular on-site visits will be performed depending on the possibility for on-site visits due to the current COVID-19 pandemic. Close-out visits are planned as on-site visits. The frequency and kind of monitoring visits will depend on the study site's recruitment rate and current situation in each country/study site. The detailed extent of the monitoring and the risk based approach considering the COVID-pandemic situation and its influence on the daily life and the health system will be defined in the overall monitoring plan applicable for all countries and in Annex 2.

8.6.3 Documentation and Data Collection

An eCRF will be prepared to report all data required by the protocol.

Site staff will transfer the study data from the source documents into the eCRF and will check eCRF entries for completeness. Completed eCRF modules will be electronically signed by an Investigator in order to ensure data entry accuracy.

Corrections to source data documents will be dated and initialed. Reasons for the corrections should be given. Corrections to eCRF entries must be electronically signed and reasons for the corrections must be provided. The date on which the correction was performed is automatically recorded by the system's audit trail.

A study monitor will review source data and the eCRF data for completeness and accuracy during the monitoring visits (source data verification (SDV)). The study monitor will point out discrepancies between source data and the data captured in the eCRF. The monitor will issue electronic queries to site staff in order to initiate discrepancy resolution. Discrepancies which require eCRF data corrections have to be resolved by authorized site personnel by answering the queries and changing the respective eCRF entries. These query management and query resolution activities are also automatically recorded by the system's audit trail.

8.6.4 Data Management

Data management will check predefined eCRF entries as defined in the data management plan (DMP) and data validation plan (DVP).

Quality control (QC) and data validation procedures such as programmed automatic edit and consistency checks ensure data validity and accuracy immediately at the point of entry into the clinical database. The database application which is used to capture electronic clinical trial data is fully CFR part 11 compliant. Thus, it is access restricted, requires electronic signatures, maintains an electronic audit trail and provides appropriate back-up functionalities. Details of the application and eCRF configuration and all further data management procedures will be described in the DMP.

The database will only be locked after all queries and discrepancies have been resolved.

After database lock, the data in the study database will be exported and transferred electronically to the responsible biometrician for statistical analysis. The export will be used to generate the patient listings, tabulations, and analyses.

Upon request safety and other reports will be generated and provided by DM to the respective members of the DSMB.

8.6.5 Archival of Documents

Sponsor will maintain the trial documents as specified in the ICH-GCP guideline and take measures to prevent accidental or premature destruction of these documents.

All documents related to the clinical trial will be retained until at least 15 years after the end of the clinical trial.

8.7 Statistical Methods Planned in the Protocol and Determination of Sample Size

8.7.1 Statistical and Analytical Plan

Details for the statistical evaluation of the results will be given in a separate statistical analysis plan.

8.7.1.1 Software to be used

All statistical calculations will be carried out using SAS language and procedures (SAS 8.2 or higher version SAS-Institute, Cary NC, USA).

8.7.1.2 Eligibility for Statistical Evaluation

Eligibility of patients will be determined within the data review meeting (blind data review meeting, DRM).

8.7.1.2.1 Safety Analysis Set (SAF)

All randomized patients who received study medication (independent of whether it is APN01 or placebo) will be valid for the SAF. The SAF will be used for the evaluation of the safety assessments (as treated).

8.7.1.2.2 Full Analysis Set (FAS)

The FAS includes all randomized subjects. The FAS serves as the primary efficacy analysis set (as randomized).

8.7.1.2.3 Per-Protocol Analysis Set (PP)

The PP includes all subjects included in the SAF who had no significant protocol deviations and completed through Day 28 or until discharge from the hospital (end of study follow-up). The PP will only be analyzed for main efficacy outcome measures (as treated).

8.7.1.2.4 Statistical Analysis

Continuous variables will be summarized with means, standard deviations, medians, lower and upper quartiles, minimums and maximums. Frequencies and percentages will be used to summarize categorical variables.

For time-to-event analyses censoring information will be used.

It is assumed that no patients will discontinue the study early prior to day 28 or hospital discharge in this Covid-19 setting. It is also assumed, that only very few missing values will arise due to not done evaluations. No imputation of missing values (e.g., no last observation carried forward (LOCF)) is planned, unless stated otherwise.

8.7.1.2.5 Primary and Secondary Endpoints

Analysis of primary efficacy endpoint

The primary endpoint of this trial is a composite of all cause-death or any use of invasive mechanical ventilation up to 28 days or hospital discharge.

Invasive mechanical ventilation is defined as patients who are intubated or have a tracheostomy tube and are receiving positive pressure ventilation. Patients who will be discharged from hospital before day 28 will be considered as non-event after confirmation by telephone interview that they are alive at day 28. Patients who will be discharged from hospital or early terminated before Day 28 will be considered having an event on the day of discharge or early termination, if a telephone interview was not possible and/or no information about alive/death status is known.

Hypothesis to be tested:

H0: $p_{APN01} = p_{Placebo}$

H1: $p_{APN01} \neq p_{Placebo}$

H0 will be tested using a Chi-squared test. The level of significance is 5% (two-sided). In addition, logistic regression analyses will be conducted considering additional co-factors (will be detailed in the statistical analysis plan).

Analysis of secondary efficacy endpoints

Secondary efficacy variables will be tested descriptively and in an exploratory manner.

1. Log transformed levels of Lactate dehydrogenase (LDH) at day 5 as a surrogate marker for organ damage

Log transformed levels of LDH will be analyzed using linear regression adjusted for baseline log levels of LDH, center and minimization factors.

95% confidence intervals will be additionally calculated.

Statistical procedures to check on a normal distributed of data, to be applied in case of non-normally distributed data, and to verify and handle minimization factors will be described in the statistical analysis plan, which will be finalized prior to unblinding.

2. 28-day mortality (all cause death)

The percentage of patients who have died at Day 28 will be presented by treatment group. Patients who will be discharged from hospital or early terminated before Day 28 will be considered having an event on the day of discharge or early termination, if a telephone interview was not possible and/or no information about alive/death status is known. The Chi-squared or Fisher's exact test will be used to compare proportions. 95% CIs will be additionally calculated. Logistic regression analyses will be conducted considering additional co-factors (will be detailed in the statistical analysis plan).

3. Ventilator-free days (VFD) up to 28 days or hospital discharge

VFD will be analyzed for both all patients as well as for the subgroup of patients who were alive at Day 28 or hospital discharge. For the analysis of all patients separate analyses will be conducted for patients who died: a) VFD will be set to 0, b) the observed VFD until death will be considered. Summary tables will be generated the VFD will be compared using Wilcoxon rank sum test. In addition, bootstrap methods will be applied to calculate 95% confidence intervals and two-sided p-values for the difference in means.

4. Proportion of responders, defined as ≥ 2 improvement in WHO's 11-Point Score system at day 7, 10, 14 and 28

Similar analyses as for 28-day mortality will be conducted.

5. Time to death (all cause) will be analyzed using Kaplan-Meier estimates and plots, log-rank test, and Cox proportional hazards model (adjusted for minimization factors to derive hazard ratios and corresponding 95% confidence intervals). Patients who will be alive at Day 28, or who will be discharged from hospital before day 28 with no information on death until day 28, will be censored at discharge if they cannot be reached at or after day 28 by means of a telephone interview. Further details will be described in the statistical analysis plan.

6. Proportion of patients with any use of invasive mechanical ventilation up to 28 days or hospital discharge

Similar analyses as for 28-day mortality will be conducted.

7. Time to first use of invasive mechanical ventilation up to 28 days or hospital discharge
Similar analyses as for time to death will be conducted. Patients without invasive mechanical ventilation will be censored on the last day of evaluation. For patients who died the observed time to first use of invasive mechanical ventilation will be considered; if a patient who died did not receive any mechanical ventilation, the patient will be censored on time of death.

8. Absolute values and absolute change in P/F ratio over time

The PF ratio is defined as PaO₂ [mmHg] divided by FiO₂ in [%] and will be evaluated on each visit. Summary statistics for the PF ratio for both the absolute values and the absolute change from Baseline (day 1) will be tabulated.

9. Absolute values and absolute change in the modified Sequential organ failure assessment score (mSOFA score) over time

Similar analyses as for the PF ratio will be conducted.

10. Time to a 2-point decrease in WHO scoring scheme.
Similar analyzes as for 28-day mortality will be conducted. Patients without ≥ 2 improvement in WHO's 11-Point Score system will be censored on the last day of WHO scoring evaluation. For patients who died the observed time to a 2-point decrease until death will be considered; if a patient who died no 2-point decrease was observed, the patient will be censored on time of death.

11. Absolute values and absolute change in lymphocyte counts over time

Summary statistics for both the absolute values and the absolute change from Baseline (day 1) will be tabulated.

12. Absolute values and absolute change in C-reactive protein levels over time

Summary statistics for both the absolute values and the absolute change from Baseline (day 1) will be tabulated.

13. Absolute values and absolute change in D-dimer over time

Summary statistics for both the absolute values and the absolute change from Baseline (day 1) will be tabulated (prognostic information: Zhou et al. Lancet 2020).

14. Absolute values and absolute change in log transformed levels of LDH over time

Summary statistics for both the absolute values and the absolute change from Baseline (day 1) will be tabulated.

15. Time to hospital discharge

Similar analyses as for time to death will be conducted. Patients without hospital discharge will be censored on the last of hospital stay. Patients who died in the hospital will be censored on the day of death.

16. Change in viral RNA over time

Summary statistics for both the absolute values and the absolute change from Baseline (day 1) will be tabulated.

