Proportion of patients with any use of invasive mechanical ventilation (up to 28 days or hospital discharge)

Requirement and type of ventilation will be presented using frequency tables.

Chi-squared test or Fisher’s exact test

Proportion of responder, i.e. those patients that having an invasive mechanical ventilation (up to 28 days or hospital discharge), as well as the p-value (two-sided) will be reported.

Logistic regression

The following co-factors will be included in the logistic regression:

- Arterial hypertension
- Diabetes
- Coronary artery disease
- Age (<65 years vs. >=65 years)
- Center

The odds ratio along with its associated 95% confidence intervals will be reported.

Time to first use of invasive mechanical ventilation (up to 28 days or hospital discharge)

Time to first use of invasive mechanical ventilation [days] = Start date of first ventilation - Date of randomization.

If ventilation started before randomization, the time to first use will be set to 0 (minimal possible duration).

Patients without documented invasive mechanical ventilation who completed the study or was early terminated or discharged from hospital before Day 28 will be censored at the date of study completion, discontinuation or discharge from hospital respectively.

Time to first use of invasive mechanical ventilation (up to 28 days or hospital discharge) will be analyzed using Kaplan-Meier estimates and plots, log-rank test, and Cox proportional hazards model (adjusted for center and age to derive hazard ratios and corresponding 95% confidence intervals).

Kaplan-Meier estimates and Log-rank test

Kaplan-Meier table (product-limit “survival” estimates with 95%-CI, Standard error, Number of patient with event, Number of patient at risk) for Time to first use of invasive mechanical ventilation [days], Kaplan-Meier Summaries of Event/Censoring (Number of patient with event, Number of patient censored, Total number of patients), Quartile Estimates (Median Time to Event, 1st Quartile, 3rd Quartile, 95%-CI) and Kaplan-Meier table (“survival” estimates with 95%-CI) for Timepoint (28 days). Time to first use of invasive mechanical ventilation [days] will be displayed by a Kaplan-Meier-curve. Treatments groups will be compared with Log-rank test.

Cox proportional hazards model

The hazards ratio along with its associated 95% confidence intervals as well as parameter estimate and p-value (two-sided) will be reported.

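### The planned 28-day Kaplan-Meier figure for first invasive ventilation censors deaths and discharges, so it overstates the risk by an amount the documents do not fix

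*Protocol*

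**What the plan says.** Secondary endpoint 7 is the time to first invasive mechanical ventilation, in a window that closes at day 28 or at hospital discharge.

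The two documents state the censoring differently:

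- **Protocol 8.7.1.2.5.** The general rule is "Patients without invasive mechanical ventilation will be censored on the last day of evaluation". For deaths, "if a patient who died did not receive any mechanical ventilation, the patient will be censored on time of death". Discharge is not named.
- **SAP 4.4.2.** For patients with no documented ventilation, whether they finished the study or not, the rule reads: "was early terminated or discharged from hospital before Day 28 will be censored at the date of study completion, discontinuation or discharge from hospital respectively". Death is not named.

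On method, the SAP states: "Time to first use of invasive mechanical ventilation (up to 28 days or hospital discharge) will be analyzed using Kaplan-Meier estimates and plots, log-rank test", plus a Cox model adjusted for center and age. The Kaplan-Meier output includes quartiles of time to event and a survival estimate "for Timepoint (28 days). Time to first use of invasive mechanical ventilation [days] will be displayed by a Kaplan-Meier-curve". Neither document mentions cumulative incidence or competing risks, and SAP section 5 (Changes from Protocol) lists nothing for this endpoint.

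Endpoint 6 covers the same patients and window as a simple proportion: "those patients that having an invasive mechanical ventilation (up to 28 days or hospital discharge), as well as the p-value (two-sided) will be reported".

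**The concern.** Kaplan-Meier treats a censored patient as someone who could still have the event later, at the rate seen in those still under observation. Here that is untrue by definition. A patient who has died cannot be intubated, and a patient who has gone home has left the window in which the endpoint counts ventilation. Censoring them passes their probability to patients who remain in hospital, so one minus Kaplan-Meier is pushed above the share actually ventilated.

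Two things are at stake. First, the report would carry two 28-day ventilation figures for the same patients, one from endpoint 6 and one from endpoint 7, with nothing to explain the gap. Second, a plotted curve and a tabulated 28-day value will be read as absolute risk, whatever the status of the endpoint.

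**Working it through.** **The plan's own figure.** The documents give no expected value for this endpoint. The nearest figure is the sample size for the primary composite (Protocol 8.7.2): 50% versus 30%, two-sided 0.05, 80% power. With pooled variance and no continuity correction:

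n per group = [1.960·√(2·0.4·0.6) + 0.8416·√(0.5·0.5 + 0.3·0.7)]² / 0.20² = (1.3579 + 0.5708)² / 0.04 = 93.

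This reproduces the stated 93 per group. It does not involve endpoint 7.

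**Direction of the bias.** Let h_v, h_d and h_q be the daily hazards of ventilation, death without ventilation and discharge without ventilation, with L their sum.

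- Share ventilated by day 28 or discharge: (h_v/L)·(1 − e^(−28L)).
- One minus Kaplan-Meier with death and discharge censored: 1 − e^(−28·h_v).

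| Assumed h_v / h_q / h_d | Share ventilated | 1 − Kaplan-Meier |
|---|---|---|
| 0.03 / 0.05 / 0.01 | (0.03/0.09)(1 − e^−2.52) = 31% | 1 − e^−0.84 = 57% |
| 0.015 / 0.05 / 0.005 | (0.015/0.07)(1 − e^−1.96) = 18% | 1 − e^−0.42 = 34% |
| 0.02 / 0.06 / 0.01 | (0.02/0.09)(1 − e^−2.52) = 20% | 1 − e^−0.56 = 43% |

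In the first row Kaplan-Meier would also print a median time to ventilation of ln 2 / 0.03 = 23 days, although only 31% are ever ventilated.

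**Size, tied to the plan's composite rates.** The split between ventilation and death, the share discharged and all timings are assumptions. With constant hazards and 5% still in hospital at day 28, 28·h_v = −ln(0.05)·v/0.95, where v is the share ventilated:

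- Composite 50%, 45% discharged: v of 40% / 30% / 20% gives Kaplan-Meier 72% / 61% / 47% (1.8 to 2.3 times).
- Composite 30%, 65% discharged: v of 25% / 20% / 10% gives 55% / 47% / 27% (2.2 to 2.7 times).

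Constant hazards let discharges start on day 1, which favours a large bias. Simulations of 40,000 patients with lognormal event times, on the same splits, show how much timing matters:

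| Median day: ventilation / discharge | 1 − Kaplan-Meier over actual share |
|---|---|
| 2 / 14 | 1.03 to 1.04 |
| 3 / 12 | 1.12 to 1.16 |
| 5 / 10 | 1.4 to 1.6 |
| 7 / 9 | 1.65 to 2.2 |

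**Which rule causes it.** The calculation was repeated with deaths censored but discharged patients kept at risk to day 28. The constant-hazard results fall to 1.03 to 1.21 times (for example 20% becomes 24%, and 25% becomes 26%). Censoring deaths alone therefore adds about 0 to 4 percentage points. Nearly all of the large excess comes from censoring at discharge, which only the SAP states.

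**Death without intubation.** Suppose both arms have a composite of 40% and half the patients are discharged. One arm has 30% ventilated and 10% dead unventilated; the other has 20% and 20%, with the deaths early (median day 3). Simulated Kaplan-Meier ventilation is 37% versus 27%, and the crude proportion is 30% versus 20%. Both look like a benefit where the composite shows none.

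**The case against.** The strongest reply is that little depends on this output. Secondary endpoints are declared descriptive and exploratory. Endpoint 6 already gives the crude proportion, which equals cumulative incidence if follow-up to day 28 or discharge is complete, so a correct absolute risk is already planned. Death counts against treatment in the primary analysis ("The primary endpoint of this trial is a composite of all cause-death or any use of invasive mechanical ventilation up to 28 days or hospital" …), in 28-day mortality, in time to death, and in the ventilator-free-days analysis that sets deaths to 0. All of this stands and limits the priority. It does not make the 28-day Kaplan-Meier figure correct, and having the right number beside it is what exposes the mismatch.

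A reader might also infer more than the documents support:

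- **That the overstatement is necessarily large.** The documents give no timing or split of ventilation, death and discharge. If ventilation comes in the first days and discharge in the second or third week, the excess is a few percent.
- **That different discharge or death rates between arms distort the Kaplan-Meier comparison.** With constant, independent hazards, 1 − e^(−28·h_v) contains neither rate. With h_v 0.02 and h_d 0.01 in both arms and discharge at 0.05 versus 0.08, Kaplan-Meier gives 43% in each arm, while the shares ventilated are 22% and 17%. Distortion of the curves would need informative censoring, which the documents neither establish nor exclude.
- **That the log-rank test and Cox model are invalid.** They remain valid for the cause-specific hazard of ventilation and need only that label.
- **That cumulative incidence with Gray's test makes death count as harm.** It does not. Tripling h_d from 0.01 to 0.03 in the first scenario lowers cumulative incidence from 31% to (0.03/0.11)(1 − e^−3.08) = 26%.

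**Conclusion.** The point holds in a limited form. Under the endpoint's own window, censoring deaths and discharges makes one minus Kaplan-Meier an upward-biased estimate of the 28-day ventilation risk. It will exceed the proportion in endpoint 6 whenever unventilated patients die or leave before later ventilations occur. The direction is certain. The size, about 1.03 to 2.7 times across the scenarios tried, rests entirely on assumed splits and timings.

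The size also depends on which censoring text is applied. The Protocol's last day of evaluation can fall after discharge, because Protocol 8.4.1.3 allows out-patient and home follow-up visits. On that reading the excess is at most about 1.2 times; on the SAP's reading it can exceed double. The SAP gives no explicit rule for deaths on this endpoint.

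It would be tempting to say that early death without intubation looks harmless in this trial. That is true only inside this endpoint (and endpoint 6); the primary composite and the mortality analyses count it. The primary test and the sample size are unaffected. Priority is minor to moderate.

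**What to change.** In SAP 4.4.2, for time to first invasive ventilation:

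1. Reconcile the censoring rule with Protocol 8.7.1.2.5. State one rule each for discharge, death and early termination, and record the change in SAP section 5.
2. Replace the Kaplan-Meier table, quartiles, 28-day estimate and plot with Aalen-Johansen cumulative incidence by arm, with death without ventilation and discharge without ventilation as competing events. Administrative end of follow-up and withdrawal stay as censoring. Note that the day-28 value should agree with endpoint 6 when follow-up is complete.
3. Keep the log-rank test and Cox model, labelled as cause-specific. Gray's test is optional.
4. Show time to ventilation or death beside it. This is the display that counts death without intubation as a bad outcome; cumulative incidence and Gray's test do not.

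The cost is SAP wording and a small amount of programming with standard SAS procedures. The dates of randomization, ventilation start, discharge and death are already used by other planned endpoints, so no new data are needed. The change should be made before unblinding; if that has passed, the added displays should be labelled post hoc in the study report.
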